6.8 STUDY MEDICATION ACCOUNTABILITY

The Investigator, a member of the investigational staff, or a hospital pharmacist must maintain an adequate record of the receipt and distribution of all trial medication using a Drug Accountability Form. These forms must be available for inspection at any time.

7 EFFICACY, SAFETY AND PHARMACOKINETICS MEASURES

7.1 SCHEDULE OF ASSESSMENTS

A Schedule of Assessments is presented in Appendix 1, Sections 11.1.

7.2 EFFICACY MEASURES

Primary and secondary endpoints include evaluation of efficacy by determination of the number of patients who achieve a response (i.e. CR, PR, stable disease, disease progression, or hematologic improvement). Response will be evaluated every 2 cycles or more frequently at the discretion of the investigator. Determination of disease response is based on the 2006 IWG response criteria (see Appendix 3).

7.3 SAFETY MEASURES

Safety assessments will be performed at intervals indicated in the Schedule of Assessments (Appendix 1, Sections 11.1) and at any time deemed necessary by the Investigator.

7.3.1 Physical Examination

Physical examinations may include examination of general appearance, skin, head and neck (including thyroid), eyes, ears, nose, throat, heart, lungs, chest (including breasts), abdomen, genitalia, anorectal area, musculoskeletal, lymph nodes, extremities, nervous system, and assessment of extramedullary disease. An AE form must be completed for all changes from condition at the Baseline Visit that are identified as clinically noteworthy.

7.3.2 Vital Signs

Vital signs will include body temperature (°C), pulse rates, and systolic and diastolic blood pressures. Height in centimeters (without shoes) and weight in kilograms will be recorded. Body surface area (BSA) will be calculated automatically in the eCRF at screening using the following formula: BSA is square root of (height in cm x weight in kg)/3600.

7.3.3 Electrocardiography (ECG)

Standard 12-lead ECGs will be conducted during the Screening Visit, and as indicated in the schedule of assessments (Appendix 1).

7.3.4 Left Ventricular Ejection Fraction

The left ventricular ejection fraction (LVEF) will be measured by transthoracic echocardiogram

at end of each cycle. If patient has been off tosedostat for more than 2 weeks after Day 28, then a transthoracic echocardiogram will be repeated prior to start of subsequent cycle.

7.3.5 Laboratory Parameters

The laboratory tests comprise:

- Hematology: Hgb, erythrocyte count, leukocyte count (with differential), platelet count, mean corpuscular volume, lymphocyte count, ANC
- Coagulation: PT, activated partial thromboplastin time (APTT).
- Chemistry: blood urea nitrogen (BUN), chloride, albumin, ALT, alkaline phosphatase, aspartate aminotransferase (AST), bilirubin-total, calcium, creatinine, glucose, potassium, total protein, sodium, and magnesium.
- Cardiovascular panel: Troponin I, N-terminal Prohormone Brain Natriuretic Peptide,
- Urinalysis (dipstick): pH, specific gravity, ketones, protein, glucose, bilirubin, and blood. In addition, a microscopic examination is to be performed if more than 1 test is positive.

In the event of an unexplained clinically noteworthy abnormal laboratory test value, the test should be repeated immediately and followed up until it has returned to the normal range and/or an adequate explanation of the abnormality is found.

Clinical laboratory tests will be reviewed for results of potential clinical significance at all time points throughout the study. The Investigator will evaluate any change in laboratory values. If the Investigator determines a laboratory abnormality to be clinically significant, it is considered an AE; however, if the laboratory value abnormality is consistent with a current diagnosis, it may be documented accordingly. A change in CTCAE grading of 2 or more grades in any laboratory value should be reported as an AE. All grade 3 or higher CTCAE side effects should be reported as an AE.

7.3.6 Adverse Events

The Investigator is responsible for recording all AEs observed during the study (screening, treatment and a 28-day period after last dose of study drug). Events which occur during the screening period will be considered baseline signs and/or symptoms unless caused by a study-related procedure or intervention, in which case they will be considered AEs.

Definition of AE in this study: an AE is any untoward medical occurrence in a subject administered a pharmaceutical product (or associated with a study-related procedure) and which does not necessarily have a causal relationship with this treatment.

Definition of Serious Adverse Event (SAE): an AE that:

- Results in death
- Is life-threatening (the subject is at a risk of death at the time of the event; it does not

- refer to an event which hypothetically might have caused death if it were more severe)
- Requires inpatient hospitalization or prolongation of existing hospitalization: hospital admissions and/or surgical operations planned before or during a study are not considered AEs if the illness or disease existed before the subject was enrolled in the study, provided that it did not deteriorate in an unexpected way during the study
- Results in persistent or significant disability/incapacity
- Is a congenital abnormality/birth defect
- Other: medically significant events, which do not meet any of the criteria above, but may jeopardize the subject and may require medical or surgical intervention to prevent one of the other serious outcomes listed in the definition above. An example of such an event would be convulsions that do not result in hospitalization.

Each AE is to be evaluated for duration, severity, seriousness, and causal relationship to the investigational drug. The action taken and the outcome must also be recorded.

7.3.6.1 *Severity*

The severity of the AE will be defined by the CTCAE v4.0

http://evs.nci.nih.gov/ftp1/CTCAE/CTCAE_4.03_2010-06-14_QuickReference_8.5x11.pdf

7.3.6.2 *Relationship*

The causal relationship between the study medication and the AE has to be characterized as 'related' or 'unrelated' as defined below:

Related to study drug: Any AE (serious or not) that appears to have a reasonable possibility of causal relationship to the use of the study drug (i.e., a relationship cannot be ruled out). Guidelines to determine whether an event might be considered related include (but are not limited to) the following:

- The event occurred in close temporal relationship to study drug administration.
- The event abated (diminished) or disappeared when treatment with the study drug was down-titrated, interrupted, or discontinued.
- The event re-occurred when treatment was re-introduced.
- Environmental factors such as clinical state and other treatments could equally have caused the event.

Unrelated to study drug: This category applies to any AE (serious or not) that does not appear to have a reasonable relationship to the use of study drug (see above guidelines).

7.3.6.3 *Reporting of Adverse Events*

All AEs, regardless of severity and whether or not they occurred during the screening, treatment or follow-up period, are to be recorded on the appropriate AE pages (either 'serious' or 'non-serious') in the eCRF. Events which occur during the screening period will be considered baseline signs and/or symptoms unless caused by a study-related procedure or intervention,

in which case they will be considered AEs. The Investigator should complete all the details requested including dates of onset, resolution, severity, action taken, outcome, relationship to study drug. Each event should be recorded separately.

7.3.6.4 *Reporting of Serious Adverse Events to Regulatory Authorities and Investigators*

As Sponsor, Weill Cornell Medical College is responsible for ensuring the expedited reporting of serious, unexpected adverse drug reactions to regulatory authorities and IRBs/IECs. Expectedness assessments will be made by the IRB using the most current, approved Tosedostat Investigator Brochure or approved product labeling (e.g. for Azacitidine) The PI is responsible for submission of expedited reports to the IRB. A written report will be submitted to the Institutional Review Board (IRB) in accordance with the IRB's policy. SAEs should also be reported to CTI BioPharma Corp. (CTI). SAE reports [(including the voluntary MedWatch Form (Form FDA 3500) if criteria are met] should be sent to:

NAME: CTI Pharmacovigilance
FAX #: [name]
E-mail: [contact]

The study number, WCMC IST-CTI-MDS, should be referenced on the fax or subject line of the e-mail. Additional follow-up information should be completed on a SAE follow-up form as soon as it becomes available.

7.3.6.5 *Follow-Up of Adverse Events*

The Investigator will continually monitor any subject with an AE and SAE until either the event has returned to the baseline grade or \leq grade 1 or, if the AE is determined to be chronic, a cause is identified, or until the subjects starts another type of anti-neoplastic therapy.

Follow-up of all AEs must be documented in the subject's medical record and on the eCRF. A narrative outlining the details of the SAE, treatment, and outcome are to be included on the SAE form and additional information which the investigator thinks is relevant.

All Serious AEs that occur within 28 days of the last dose of study drug should also be reported to CTI BioPharma Corp. and followed up in the same manner. New SAEs assessed as causally related to Tosedostat and occurring at any time after the End-of-Study or after the 28-day follow-up period after study drug discontinuation (whichever comes first) should be reported to the Sponsor promptly after the Investigator becomes aware of the event.

7.4 *QUALITY CONTROL AND QUALITY ASSURANCE*

This study will be conducted and monitored according to GCP and training will be given to all study personnel on all relevant aspects of the protocol.

According to the Guidelines of Good Clinical Practice (CPMP/ICH/135/95), CTI BioPharma Corp. is responsible for implementing and maintaining quality assurance and quality control systems with written Standard Operating Procedures (SOPs).

Quality control will be applied to each stage of data handling.

The data collection plan for this study is to utilize REDCap to capture all treatment, toxicity, and efficacy data for all enrolled patients.

REDCap (Research Electronic Data Capture) is a free data management software system that is fully supported by the Weill Cornell Medical Center CTSC. It is a tool for the creation of customized, secure data management systems that include Web-based data-entry forms, reporting tools, and a full array of security features including user and group based privileges, authentication using institution LDAP system, with a full audit trail of data manipulation and export procedures. REDCap is maintained on CTSC-owned servers that are backed up nightly and support encrypted (SSL-based) connections. Nationally, the software is developed, enhanced and supported through a multi-institutional consortium led by the Vanderbilt University CTSA.

The PI ensures all completed CRFs and completed data correction forms are accurate.

In addition, CTI BioPharma Corp. may conduct periodic audits of the study processes, including, but not limited to investigational site, site visits, central laboratories, vendors, clinical database, and final clinical study report. When audits are conducted, access must be authorized for all study related documents including medical history and concomitant medication documentation to authorized CTI BioPharma Corp. representatives and regulatory authorities.

Additionally, as the WCM DSMB serves as the primary monitoring entity for the trial, the WCM DSMB will have access to the RedCap database to verify data integrity.

7.4.1 Safety Monitoring

This is an investigator-initiated trial. The Principal Investigator will be responsible for the study and will ensure that the protocol is being followed in accordance with current local IRB, FDA, and ICH regulations/guidelines.

In this research study, safety data is reviewed on a rolling basis. A formal safety interim analysis will take place after 40 patients have been enrolled and completed at least one cycle of treatment. The Investigator will review the following safety:

- Physical exam
- Vital signs
- Electrocardiogram (ECG)
- Left ventricular ejection fracture (LVEF)
- Laboratory parameters, includes blood counts, blood chemistries, urinalysis, coagulation, and cardiac panel
- Adverse events and serious adverse events

Based on the results of the interim analysis, the investigator may allow the study to proceed as is, modify the study, or terminate the study.

7.4.2 Data Management/Coding

Data generated within this clinical trial will be handled according to the relevant SOPs of WCMC. Adverse events and concomitant diseases should be coded using the Medical Dictionary for Regulatory Activities (MedDRA). Concomitant medications and prior MDS therapies will be coded using the WHO Drug dictionary.

7.4.3 Quality Assurance Audit

Investigator sites, the study database and study documentation may be subject to Quality Assurance audit during the course of the study by CTI BioPharma Corp. or a third party auditor on behalf of CTI BioPharma Corp. In addition, inspections may be conducted by regulatory bodies at their discretion.

7.4.4 Data Safety Monitoring Board (DSMB)

Weill Cornell Medical College requires that all research approved by the WCMC IRB include an appropriate plan for the monitoring of data to ensure the safety of human subjects. Research supported by Federal agencies will be monitored according to all regulations and guidelines of the relevant Federal agency.

The WCM Data and Safety Monitoring Board (WCM DSMB) will review the IRB approved protocol, informed consent documents, and data and safety monitoring plan (DSMP). During the course of the study, the DSMB will perform a review of initial subject safety data following the treatment of five subjects with one cycle of treatment (28 days) after approval of protocol version 1.2, and then semiannually to evaluate safety, efficacy, study conduct, and scientific validity and integrity of the trial. An interim analysis for futility will be performed after the first 40 subjects are treated, and if the median overall survival is less than three months, then we will consider discontinuing the study for futility. The WCM DSMB will review interim analysis results. Subsequent enrollement should ideally resume after completion of interim analysis, however recognizing the acute and grave nature of MDS, it might not be possible to deny treatment to potential subjects for ethical reasons sufficiently long to complete interim analysis.

Given the aggressive nature of disease and expectation of serious adverse events in this study population, if there are ≥ 8 instances of grade V events related to the study drug, then we will consider discontinuing the study for safety.^{19,21}

The WCM DSMB will also review all SAEs occurring on the trial. SAEs will be reported to the DSMB per the WCM IRB Immediate Reporting Policy:

http://researchintegrity.weill.cornell.edu/institutional_review_board/irb_adv.html. The WCM DSMB may also convene as need if stopping criteria are met or other safety issues arise

that the Principal Investigator and/or IRB would like the WCM DSMB to address. The study Principal Investigator is responsible for submitting all written DSMB recommendations to the IRB upon receipt.

8 STATISTICS

This is an open-label, phase II study designed to explore the clinical activity of tosedostat in patients with MDS who have failed therapy with hypomethylating agents. The study will include 80 patients with high and very high risk MDS with the goal of doubling median overall survival from 6 to 12 months. A futility analysis will be performed after the first 40 patients are treated, and if the median overall survival is less than 3 months, then we will consider closing the study.

Sample size considerations:

The primary endpoint for is overall survival, as measured from the start of the treatment to the date of death (or date of last follow-up if no death). Previous data suggest that the median overall survival for high risk MDS patients is 6.0 months. With the administration of tosedostat, we anticipate the median overall survival to be improved to ≥ 9 months. A sample size of 80 patients is planned for this study, which will give us at least 85% power to detect the hypothesized improvement. This calculation assumes a Type I error of 10%, a one-sided test, and a median follow-up time of 2.5 years. It also assumes that survival times are exponentially distributed. This last assumption is for planning purposes only; actual analysis will employ nonparametric methods for estimation and testing of survival distributions. A two-sided 95% confidence interval for the median overall survival is estimated to be (6.2 months, 12.7 months) under the hypothesized improvement. At an accrual rate of 3-4 patients per month, we anticipate to complete enrollment in approximately two years.

Analysis Plan:

The median overall survival will be estimated by the Kaplan-Meier method and 95% confidence intervals for overall survival estimates will be calculated using Greenwood's formula. Descriptive statistics will be utilized to describe the parameter proportions defined above (i.e., frequency, percent). Estimated differences in the transfusion independence proportion/overall survival between categories of demographic and treatment variables (evaluated by the two-sample t-test, Wilcoxon rank-sum test, Fisher's exact test, and log-rank test, as appropriate) will serve as preliminary data (i.e., hypothesis-generating) for future studies. All p-values will be two-sided with statistical significance evaluated at the 0.05 alpha level. Ninety-five percent confidence intervals will be calculated to assess the precision of the obtained estimates. All analyses will be performed in SAS Version 9.4 (SAS Institute, Inc., Cary, NC) and Stata Version 14.0 (StataCorp, College Station, TX).

Safety Analyses

Safety analysis will include AE summary tables using Medical Dictionary for Regulatory Activities (MedDRA) and NCI CTCAE criteria, changes in physical examination and performance status, ECG, and laboratory summary tables and figures.

Adverse Events

Adverse events occurring during the AE reporting period (see Section 7.3) will be summarized. They will be tabulated by SOC and by preferred term within SOC according to MedDRA. Severity will be graded using the NCI CTCAE. While the goal is to collect 28-day follow-up data, it is possible that patients may proceed to other anticancer therapies before completing the 28-day follow-up.

Exact 95% confidence intervals around the adverse event proportions will be calculated to assess the precision of the obtained estimates.

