2 STUDY OBJECTIVES

Primary Objective:

The primary objective of the study is to evaluate the safety and efficacy of tosedostat in patients with myelodysplastic syndrome who have relapsed after or are refractory or intolerant to azacitidine or decitabine. The primary endpoint for patients is overall survival.

Secondary Objectives:

The following secondary endpoints will be evaluated:

- Hematological improvements (erythroid response [ER], platelet response [PLR] and neutrophil response [NR]) according to 2006 IWG criteria (Appendix 3), including reduction in RBC and/or PLT transfusion needs
- Overall response (complete remission [CR], partial remission [PR], bone marrow complete response [BMCR], and stable disease [SD] according to 2006 International Working Group (IWG) criteria, including, among responders, the distribution of time to response and the duration of response. (Appendix 3)
- Improvements of cytogenetics as evaluated by the change in aneuploidy in BM according to 2006 IWG criteria
- Safety and tolerability of tosedostat
- Time to AML transformation

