3 INVESTIGATIONAL PLAN

3.1 CLINICAL STUDY DESIGN AND PLAN

This is a single-center, open label, phase II study of clinical activity of tosedostat in adult patients with MDS who have failed prior hypomethylating agent-based therapy. In this study, approximately 80 patients (80 patients;) will be enrolled at Weill Cornell Medical College. The dose of tosedostat will be 120 mg once a day continuously for each 28 day treatment cycle.

The dose of tosedostat should be taken orally with a glass of water after food preferably in the morning at about the same time every day to ensure an even dose interval.

Patients will be assessed for disease response every two cycles as defined in the protocol. If patient has no response as defined by the protocol after two cycles, azacitidine 75 mg/m² SC or IV for 5 days may be combined with tosedostat, at the investigator's discretion.

Subjects will be permitted to interrupt tosedostat treatment, to a maximum of 14 days, under circumstances described in Section 6.5. If a subject requires multiple, or prolonged (greater than 14 days) study medication interruptions, the principal investigator will be consulted for a discussion on the subject's continued participation in the study. Investigators are encouraged to avoid unnecessary subject withdrawal. Late response to therapy has been seen in earlier trials, particularly in those who have shown at least stabilization of disease. However, the safety of the subject is paramount and subject's right to withdraw at any time is absolute.

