3.2 DISCUSSION OF STUDY DESIGN

While the prognosis of MDS patients who are refractory to or have relapsed after treatment with hypomethylating agents is universally poor. For higher risk MDS patients, overall survival is extremely short, with estimates ranging from 3-6 months. Therefore, for this group, the primary endpoint is doubling of overall survival from 6 to12 months. The tosedostat dose of 120 mg per day for this study was chosen based safety, efficacy and convenience established in the prior studies CHR-2797-002 and OPAL. Based on preliminary clinical and in vitro data, it is possible that tosedostat may synergize with and/or restore sensitivity to the hypomethylating agent azacitidine. Therefore, for patients who have stable disease, but no hematological improvement after 2 cycles with tosedostat, the investigator may add azacitidine 75 mg/m² IV or SC for 5 days to tosedostat.

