6.3 ADDITION OF AZACITIDINE FOR NON-RESPONSE

If at end of two cycles of tosedostat, patient does not have response as defined as above, the investigator has discretion of adding azacitidine in addition to tosedostat. Dosing will be standard dosing (azacitidine 75mg/m²), either subcutaneously or intravenously, for 5 continuous days every 28 days.

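### Section 8 does not mention the optional azacitidine add-on, so the planned response proportions mix tosedostat-alone and combination responses, and overall survival is labelled as a tosedostat effect

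*Combined protocol and SAP*

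**What the plan says.** The objective in Section 2 names one drug: "The primary objective of the study is to evaluate the safety and efficacy of tosedostat in patients with myelodysplastic syndrome". Section 7.2 counts responders: "Primary and secondary endpoints include evaluation of efficacy by determination of the number of patients who achieve a response". Response is assessed every two cycles, and no rule stops the count when azacitidine starts.

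The add-on appears in three places. Section 3.1 opens it "If patient has no response as defined by the protocol after two cycles". In Section 6.3, after two cycles without response, "the investigator has discretion of adding azacitidine in addition to tosedostat". Section 3.2 describes it "for patients who have stable disease, but no hematological improvement after 2 cycles with tosedostat", and gives the reason: "it is possible that tosedostat may synergize with and/or restore sensitivity to the hypomethylating agent azacitidine".

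Section 5.7.4 requires tosedostat to stop for lack of response after four cycles alone, or after four cycles of azacitidine if it was added. It also requires tosedostat to stop on disease progression. Section 4.3 allows up to four cycles for a response to tosedostat. Section 5.2.2 says that patients with CR, PR, hematologic improvement or stable disease at the end of cycle 2 may continue.

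Section 8 does not mention azacitidine. On proportions it says "Descriptive statistics will be utilized to describe the parameter proportions defined above", by frequency and percent. On survival it says "With the administration of tosedostat, we anticipate the median overall survival to be improved". It also plans exploratory comparisons of transfusion independence and overall survival across unnamed treatment variables.

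**The concern.** A second active drug, which the protocol itself thinks may help, can enter after cycle 2. If it starts in cycle 3, a patient may first respond as late as cycle 2 + 4 = 6. A plain count of responders then pools two regimens and two response windows.

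The split could be recovered later, because Section 7.4 says all treatment and efficacy data are captured. But it is not pre-specified. In an open-label single-arm trial with a discretionary add-on, a single mixed rate could be reported as tosedostat activity, or the split could be chosen after the results are known. A survival gain could likewise be credited to tosedostat when part of it came from azacitidine or from the combination.

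**Working it through.** **The plan's own figure.** Section 8 states at least 85% power for a median of 9 against 6 months, with n = 80 and a one-sided 10% error. A test of survival at 6 months reproduces it: p0 = 0.50, p1 = 0.5^(6/9) = 0.630, and power = Φ[(√80 × 0.130 − 1.2816 × 0.5) / √(0.630 × 0.370)] = Φ(1.08) = 0.860. This point does not dispute that figure.

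**Inputs for the response illustration**
- OPAL study, AML, both dose cohorts (Section 1.1.4.2; 38 + 35 = 73 patients from Table 2): 16/73 with PR or better, 21/73 with stable disease, median time to response 56 days.
- From that median, half of the tosedostat responses are taken as early (by day 56) and half as late: 8/73 = 0.110 each. Late responders are assumed to be stable at day 56.
- Add-on uptake u = 0.3-0.7: assumed.
- Add-on response r = 0.1-0.3: assumed. The upper end is 3 of 10 from Section 1.1.4.4, where azacitidine ran for 7 days rather than 5 and all subjects received it with tosedostat. Here it would go to patients who had already failed two cycles of tosedostat, so a lower end is needed.
- Progressed patients must stop tosedostat (Section 5.7.4), so only patients stable at day 56 are taken as eligible.

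**Formulas**
- Eligible = (21 + 8)/73 = 0.397, or 31.8 of 80.
- Rate before azacitidine = 0.110 + 0.110 × (1 − u).
- Combination responses = 0.397 × u × r.
- Mixed rate = the sum of the last two.

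| u | r | Before azacitidine | Combination (of 80) | Mixed rate | Combination share |
|---|---|---|---|---|---|
| 0.3 | 0.1 | 0.186 | 0.012 (1.0) | 0.198 | 6% |
| 0.7 | 0.1 | 0.142 | 0.028 (2.2) | 0.170 | 16% |
| 0.3 | 0.3 | 0.186 | 0.036 (2.9) | 0.222 | 16% |
| 0.7 | 0.3 | 0.142 | 0.083 (6.7) | 0.226 | 37% |

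The mixed rate of 17-23% lies close to the 16/73 = 22% taken for tosedostat alone, so the total by itself would not reveal the mixture.

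**Survival label.** Suppose tosedostat has no survival effect (exponential, median 6 months), so that 0.809 are alive at day 56. Suppose also that the add-on multiplies the later death hazard by 0.7-0.8 (assumed). The share of day-56 survivors who receive azacitidine is u × 0.397/0.809. I simulated 20,000 trials per setting with n = 80, 24 months of accrual and a cut-off at 42 months. The test is a one-sample log-rank against a median of 6 months: Z = (E − O)/√E, where O is observed deaths and E is deaths expected under that median. Section 8 says only that nonparametric methods will be used, so this test is a choice.

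| | True median (months) | Success, one-sided 10% | Success, two-sided 5% |
|---|---|---|---|
| No azacitidine effect | 6.0 | about 9% | about 2% |
| Hazard ratio 0.8, u 0.3-0.7 | 6.1-6.3 | 14-22% | 4-7% |
| Hazard ratio 0.7, u 0.3-0.7 | 6.2-6.5 | 18-35% | 5-14% |

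Both error levels are shown because Section 8 plans the sample size at one-sided 10% but calls all p-values two-sided at 0.05. Such a success would be right for the strategy and wrong for tosedostat alone.

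**The case against.** **Section 8 already allows comparisons by treatment variables, and the add-on is an obvious candidate in a single-dose trial.** This stands in part. The sentence permits such a comparison of survival and transfusion independence. It does not name the add-on and does not cover response. Run as a log-rank test from day 1, it would carry immortal-time bias, because only patients alive at the end of cycle 2 can receive azacitidine.

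**The survival part is only a label.** This stands. The sentence about the expected gain is a planning statement, the add-on is disclosed elsewhere, and a gain through restored sensitivity would be partly a tosedostat effect. A reader might infer that the survival analysis is invalid or that the plan instructs crediting combination responses to tosedostat. The documents support neither: counting all deaths is correct for the strategy, and no passage gives such an instruction. The mixing arises by default.

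**The add-on can reach fewer patients than Sections 3.1 and 6.3 suggest.** This stands. A reader might take every non-responder alive at day 56 as eligible, about 56 to 61 of 80, and obtain much larger figures. That ignores Section 5.7.4, which stops tosedostat on progression, and Section 5.2.2, which limits continuation. Read with those, Sections 3.1 and 6.3 come close to Section 3.2, and the conflict is mainly one of wording.

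**Stable disease is a different matter.** This stands. A reader might count it as response and move the OPAL data from 16/73 (22%) to 37/73 (51%). Section 8 prescribes no such pooled rate, and the list in Section 7.2 also contains disease progression, so it reads as categories to tabulate.

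**Conclusion.** The point holds as a cheap improvement. As written, the planned response and hematologic improvement proportions mix tosedostat-alone and combination responses under a tosedostat objective. Overall survival measures tosedostat with optional azacitidine and should be described that way.

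That conclusion rests on the text alone. Its size cannot be derived from the documents, because uptake and add-on effect are not given. The figures of 1 to 7 combination responders in 80 (6-37% of responses) and of 14-35% survival success at one-sided 10% (4-14% at two-sided 5%) depend on the assumed uptake, response rate and hazard ratios, on AML data standing in for MDS, and on the half-early split. Sample size, power and the primary survival estimate are unaffected.

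**What to change.** In Section 8:

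1. Report response and hematologic improvement first documented before the first azacitidine dose, with all treated patients as denominator and exact confidence intervals. Put responses first reached on the combination in a separate row beside the overall rate. Split time to response and duration of response in the same way.
2. State the survival conclusion for tosedostat with optional azacitidine, and report how many patients received azacitidine and when.
3. If survival is compared by add-on use, take a landmark at the end of cycle 2 among eligible patients, or a time-dependent covariate. Label the result descriptive and still confounded by indication.
4. Reconcile the wording on the add-on trigger (Sections 3.1 and 6.3 against 3.2, read with 5.2.2 and 5.7.4) and on the response window (4.3 against 5.7.4), so that the split is well defined.

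Separately, reconcile whether stable disease counts as a response (Sections 3.1.4 and 5.2.2 against 5.7.4 and Appendix 2).

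The cost is one paragraph and one table, built from treatment start, azacitidine start and response dates. The downside is that the rate before azacitidine is a lower bound, because the add-on cuts off late tosedostat responses; the overall rate should therefore stand beside it. It is also imprecise: in the illustration it is 11 to 15 of 80, with exact 95% intervals of 7-23% for 11 and 11-29% for 15.
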